## 6.6 Reminders concerning completing, revising, and submission of survey form

### [1] Completing

The doctor shall, upon confirming the survey items, complete the survey form based on medical charts and other medical records such as relevant test results, using a pen, or ballpoint pen.

### [2] Revising

Upon receiving Sponsor's inquiry on the contents of the survey form (resurvey), the investigator will again confirm the contents of medical records described earlier, and as required, correct relevant contents and resubmit the form. Corrections in the survey form should be struck out with a double line (=) with a "correction seal" on the double line; the double line should be drawn so that the original contents prior to correction are legible.

### [3] Submission method

Survey forms should be submitted promptly upon completion in accordance with the procedures set out by Sponsor.

## 7 Survey items and schedule

This Surveillance should be conducted in accordance with the following observation schedule.

Survey item	Observation period	Subject	Registration form	Survey form								
				Booklet 1 *6				Booklet 2	Booklet 3	Booklet 4		
				Pre-dose*1 During treatment*2	Start of surveillance	Month 1	Month 3	Month 6	Month 12	Month 24	Month 36	
Registration form	Confirmation of target patients, prior treatment of MTX, drugs to be investigated, ID number, patient's initials, gender, date of birth or age at the start of treatment, and start date of treatment (or surveillance)	Xeljanz group Control group	Xeljanz group	●	-	-	-	-	-	-	-	
	Contraindication, tuberculosis check, hepatitis B virus test, and clinical laboratory	Xeljanz group		●	-	-	-	-	-	-	-	
Survey Form	Patient characteristics	Both groups	Xeljanz group	-	●	-	-	-	-	-	-	
	Dose record	Both groups		-	↔							
	Concomitant therapy (Pharmacotherapy)	Xeljanz group		-	↔							
	Pneumococcus vaccination*3	Both groups		-	↔							
	Prophylactic administration*4	Both groups		-	↔							
	Chest X-rays or CT	Xeljanz group		-	●	↔		●	●	●	●	
	Tuberculosis check	Xeljanz group		-	●	-	-	-	-	-	-	
	Hepatitis B/C virus test	Xeljanz group		-	●							
	Blood pressures (systolic/diastolic)	Xeljanz group		-	●	-	-	●	●	●	●	
	Clinical laboratory	Xeljanz group		-	●	●	●	●	●	●	●	
	Tender/swollen joint count, patient/doctor-reported outcome, CRP, and ESR	Xeljanz group		-	●	-	-	●	●	●	●	
	Adverse events*5	Xeljanz group		-	↔							
		Control group		-	Serious infection			↔				
	Tests/examinations related to adverse events	Xeljanz group		-	↔							
Follow	Follow-u*6	Both groups		-	Periodically performed for 3 years from the start of treatment for subjects who prematurely discontinue treatment*6							

●: Essential data

\*1: Patients in the Xeljanz group should be registered in principle no later than 1 week prior to the start of treatment.

\*2: Patients in the control group should be registered in principle no later than 2 weeks after the start of surveillance.

\*3: Information on patients in the control group should be collected until 12 months after the start of surveillance.

\*4: Prophylactic administration to prevent tuberculosis, pneumocystis jiroveci pneumonia, and hepatitis B (nucleic acid analogs)

Information on patients in the control group should be collected until 12 months after the start of surveillance.

- Treatment start to Month 6: Malignant tumor and serious infection

\*5: All adverse events in the Xeljanz group are subject to reporting.

In the control group, the following adverse events are subject to reporting.

- Serious infections: For 12 months from the start of surveillance

- Malignant tumor and adverse events leading to death: For 36 months from the start of surveillance

\*6: For patients in the Xeljanz group (“1) Xeljanz group (2) in 6.5 observation period”) after the registration of patients in the control group is completed; only information until 6 months after the start of surveillance (Booklet 1) should be collected and no follow-up surveillance will be conducted.

## 7.1 Assessment variables

### 1) Registration items

For pre-treatment information (including the start date of the treatment), all items for the Xeljanz group and items [1] to [7] for the control group will be completed.

#### (1) Patient characteristics

##### [1] Confirmation of target patients

If the patient meets the conditions for target patients (answer “Yes”):

Timing of MTX treatment, weekly dosage at the prior treatment of MTX

If the patient does not meet the conditions for target patients (answer “No”):

[Only patients in the Xeljanz group] Reason for non-conformity with guidelines, reason for treatment of Xeljanz

##### [2] Drugs to be investigated

- Xeljanz group: Patient category :Newly prescribed, transferred from clinical study, or prescribed at other medical facility (name of the medical facility)

Control group: Pharmacotherapy: whether or not MTX has been administered, whether or not biological preparations have been administered, whether or not disease-modifying antirheumatic drugs (DMARDs) or immunosuppressants have been administered

##### [3] ID number

##### [4] Patient's initials (as necessary)

##### [5] Gender

##### [6] Date of birth (Western calendar) or age at the treatment start

##### [7] Start date of treatment (surveillance)

- Xeljanz group: Since registration takes place before treatment, the scheduled date of treatment start should be recorded.
- Control group: For registration after surveillance start, write in “start date of surveillance.”

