#### 2) Control group: A certain sample size a) b) of $\geq 2000$ subjects for safety analysis

#### [Remarks]

a) The sample size in both groups will be set to be the number of subjects for whom the degree of statistical accuracy described in [Rationale for sample size] is maintainable. See the Appendix for more information.

b) The registration period until a certain sample size is reached will be the same period for both groups.

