#### [Rationale for sample size]

The incidence of malignant tumor associated with Xeljanz in a domestic long-term administration study (Study No. A3921041) was 1.16 (/100 person-year). The drop-out rate in clinical studies was 31% among subjects who transferred from the domestic Phase II study (Study No. A3921039) to the domestic long-term administration study (Study No. A3921041) (treatment period: approximately 3 years), and 14% among subjects who transferred from another domestic Phase II study (Study No. A3921040) (treatment period: approximately 1.4 years); based on which, the drop-out rate at the completion of 3-year observation in daily medical practice is estimated to be approximately 50%.

If 4000 patients were to be enrolled in the Xeljanz group, the target events should be confirmable in 104 patients based on the incidence of malignant tumor in Japanese subjects, which was 1.16 (/100 person-year).

Next, assuming that 4000 patients would be enrolled in the Xeljanz group and the incidence of malignant tumor in the control group would be equivalent to the Xeljanz group, at least 2000 subjects would need to be enrolled in the control group in order to enable a statistically appropriate inter-group comparison; thus, a sample size of 2000 subjects was selected for control.

Depending on the progress of registration, if the registered number of patients in either group significantly exceeds the above number earlier than the other group, a sample size with 3-year observation period can be changed to the combination of a sample size for whom the degree of statistical accuracy is maintainable if it is compared with 4000

patients in the Xeljanz group and 2000 patients in the control group (see the Appended Table). Also, the registration period for patients in the inter-group comparison needs to be the same.

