### 6.3 Contract and logistics

A contract for this Surveillance must be concluded in writing with the head of each site. Contract templates of surveillance site shall be used if available.

[1] The Medical Representative (hereinafter referred to as "MR") shall provide Xeljanz Proper-use Information to doctors, pharmacists, and other relevant site staff who will handle/use Xeljanz.

[Safety information kit]

Product Summary, Proper Use Guide, explanation of "Precautions" for new pharmaceuticals, literature for use by patients, package inserts, etc.

[2] Sponsor will explain the proper use of Xeljanz to each investigator taking part in this Surveillance; after which, the investigator will sign or name/seal the "Confirmation of Cooperation to Surveillance", and submit it to the MR (this document is also required when the investigator is relocated to another site).

[Confirmation of Cooperation to Surveillance]

- Cooperation to diagnosis and treatment of serious infection, tuberculosis and malignant tumor
- Requirements for sites and doctors
- Other relevant items requiring confirmation
- Signature or name/seal of the investigator taking part in this Surveillance

[3] Upon receiving "Confirmation of Cooperation to Surveillance," a contract for this Surveillance will be concluded between the site and Sponsor.

[4] The sample size ratio between the Xeljanz group and the control group to be specified in the contract will be in principle 2 to 1. However, depending on the conditions at the medical facility, the case ratio may be adjusted between 2:1 and 1:1.

[5] Sponsor, upon confirming the conclusion of contract for this Surveillance, shall set up logistics necessary to deliver Xeljanz to the site.

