## Appendix

### “3. Target sample size”

A list of combinations for “certain sample size” in the Xeljanz and control groups

Sample size for safety analysis in “3. Target sample size” g)			
“Certain sample size h) that requires 3-year observation		6-month observation	
(1) Sample size in the control group	(2) Sample size in the Xeljanz group	(3) Sample size in the Xeljanz group	(4) Sample size in the Xeljanz group Total [(2)+(3)]
2000	4000	0	4000
2050	3814	186	4000
2100	3653	347	4000
2150	3511	489	4000
2200	3385	615	4000
2250	3273	727	4000
2300	3173	827	4000
2350	3082	918	4000
2400	3000	1000	4000

g) Subjects who meet the conditions described in “2. Subjects”.

h) A “certain sample size” will be reached when both the sample size in the control group and the sample size in the Xeljanz group exceed the number of subjects in any line of the combination of (1) and (2).

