### 6.3. Covariates

For both the Xeljanz and control groups, candidate covariates related to the development of malignant tumors and serious infections are shown below.

Covariates	Malignant tumor	Serious infection
Sex	○	○
Age	○	○
Weight	○	○
Stage of rheumatoid arthritis	○	○
Class of rheumatoid arthritis	○	○
Duration or disease	○	○
Past history (infection)	×	○
Past history (malignant tumor)	○	×
Past history (lung disorder)	×	○
Past history (interstitial pneumonia)	×	○
Complication (infection)	×	○
Complication (malignant tumor)	○	×
Complication (hepatitis B)	○	×
Complication (hepatitis C)	○	×
Complication (diabetes mellitus)	×	○
Smoking history	○	○
Family history of malignant tumors (including lymphoma)	○	○
History of MTX use (Within 3 months prior to the start of survey)	○	○
MTX criteria	○	○
History of oral steroid use (Within 3 months prior to the start of survey)	○	○
History of tacrolimus use (Within 3 months prior to the start of survey)	○	○
Past use of biological agents (Within 3 months prior to the start of survey)	○	○

Covariats	Malignant tumor	Serious infection
Initial dose of Xeljanz	○	○
Neutrophil count	○	○
Lymphocyte count	○	○
Prophylactic administration to prevent tuberculosis	×	○
Prophylactic administration to prevent pneumocystis jiroveci pneumonia	×	○
Prophylactic administration to prevent hepatitis B	×	○
DAS28	○	○

○: Applicable, ×: Not applicable

Covariates may be added or removed based on the results of the interim analyses of this survey and newly obtained findings. In that case, this plan will be revised.

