**Table 7. Definitions in the Comparison of Deaths**

Term	Definition
Survivors	Patients who do not correspond to the each definition of deaths
Time to death (overall observation period)	Date of the death - date of the initiation of treatment + 1
Censoring period for survivors (overall observation period)	Xeljanz group: Date of completion or discontinuation of follow-up - date of the initiation of treatment + 1
Time to death (treatment period)	Xeljanz group: Date of the death - date of the initiation of treatment + 1
Censoring period for survivors (treatment period)	Date of the completion of treatment - date of the initiation of treatment + 1

• **Mortality rate**

The number of patients with deaths in each group, incidence, and the 95% confidence interval will be calculated in accordance with [Section 8.1.5](#).

In addition, the incidence ratio and the 95% confidence interval and the difference in incidence rate and the 95% confidence interval will be calculated.

- **Incidence proportion of deaths**

The number of patients with deaths in each group, the incidence proportion, and the 95% confidence interval will be calculated in accordance with [Section 8.1.5](#).

In addition, the ratio of incidence proportion and the 95% confidence interval and the difference in incidence proportion and the 95% confidence interval will be calculated.

- **Analysis of time to death**

Time to death in each group will be summarized in accordance with [Section 8.1.4](#). As for the censoring period insurvivors, [Table 7](#) will be followed.

- **SMR**

Using the number of deaths in each group, the SMR and its 95% confidence interval with the Japanese as the reference population are calculated according to Section 8.1.6. The expected number of deaths is calculated using the population and deaths by gender, age and calendar year. If there is no reference population and death in the applicable calendar year, use the reference population and death by gender and age in the latest year.

Similarly, it is calculated for non MTX adherent safety analysis set.

For Japanese data, refer to the general counter of e-Stat official statistics, and calculate the expected number of deaths using the population and the number of deaths in the Vital Statistics Survey.

CC1 [REDACTED]  
[REDACTED]  
C [REDACTED]  
C [REDACTED]  
I [REDACTED]

CCI [REDACTED]

[REDACTED]

• CCI [REDACTED]

[REDACTED]

CCI [REDACTED].

• CCI [REDACTED]

[REDACTED]

CCI [REDACTED]

CCI [REDACTED]

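### Both groups must share one registration period but may fill it at different speeds, and calendar time of start is missing from the covariates behind the visible between-group estimates

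*Protocol*

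**What the plan says.** Protocol section 7.1 collects the start date at registration in both groups, as item [7], "Start date of treatment (surveillance".

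Protocol section 3 fixes a common window: "The registration period until a certain sample size is reached will be the same period for both groups". The sample-size rationale repeats this for the comparison: "the registration period for patients in the inter-group comparison needs to be the same".

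Within that window the pace may differ. The rationale provides for the case "if the registered number of patients in either group significantly exceeds the above number earlier than the other group", and then allows a different combination of group sizes. The Appendix lists nine combinations, from 4000 Xeljanz and 2000 control to 3000 and 2400. Under footnote h the target "will be reached when both the sample size in the control group and the sample size in the Xeljanz group exceed the number of subjects" of one line. Protocol section 6.3 sets the contracted split at 2:1 in principle, but "the case ratio may be adjusted between 2:1 and 1:1".

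SAP section 6.3 opens its table for both groups by saying that "candidate covariates related to the development of malignant tumors and serious infections are shown below". The 29 rows include no start date, calendar year or registration period. The propensity score (SAP 8.1.6), the adjusted hazard ratios and the single-factor pooled estimates (SAP 8.2.3.1.1 and 8.2.3.1.2) all refer to that list.

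Calendar year appears only in the external comparisons. For the SMR, "The expected number of deaths is calculated using the population and deaths by gender, age and calendar year"; one version of the SIR is built in the same way.

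**The concern.** A shared window fixes the first and last possible start dates, not how each group is spread between them. The groups also enter by different routes (Protocol section 6.4). Xeljanz is an all-cases registration made before prescribing, with checks for unregistered patients. Controls are registered by investigators up to two weeks after start. A control patient who later receives Xeljanz is registered again in the Xeljanz group, necessarily with a later start.

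If one group starts earlier on average, and infection prevention, patient selection or event reporting changes meanwhile, part of the between-group ratio reflects when patients started rather than what they received. Comparing malignancy and serious infection with the control group is a stated objective, so those are the ratios at stake. Serious infection is more exposed, because its comparison covers only one year and year of start therefore tracks time at risk closely.

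**Working it through.** **The plan's own figures.** Inputs from Protocol section 3: 1.16 malignancies per 100 person-years and about 50% drop-out at 3 years. With linear drop-out, 4000 × 3 × (1 + 0.5)/2 = 9000 person-years, and 9000 × 0.0116 = 104.4 events, matching the stated 104. The Appendix lines hold 1/n(control) + 1/n(Xeljanz) at 1/2000 + 1/4000 = 0.00075, and all nine reproduce to within one patient. They preserve precision and say nothing about timing.

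**Bias formula.** Split the window into early and late. Let p1 and p0 be the shares of Xeljanz and control patients who start early, and R the late-to-early event rate ratio. With no drug effect, the crude ratio is

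B = [p1 + (1 − p1)R] / [p0 + (1 − p0)R].

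B = 1 if p1 = p0 or if R = 1. The documents give none of p1, p0 or R, so all values below are assumptions.

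**Within the contract band.** Suppose the Xeljanz-to-control ratio stays between 2:1 and 1:1 throughout.

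- On the 4000:2000 line the overall ratio is 2:1, so the band forces 2:1 at all times and B = 1.
- On the 3000:2400 line, take 2:1 early and 1:1 late. This requires 1200:600 early and 1800:1800 late, so p1 = 1200/3000 = 0.40 and p0 = 600/2400 = 0.25. At R = 0.8, B = 0.88/0.85 = 1.035. At R = 0.5, B = 0.70/0.625 = 1.12.
- For any mix, the early odds in the two groups differ at most 2-fold. B is then largest when p0/(1 − p0) = √(R/2):

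| R | p0 at maximum | Largest B |
|---|---|---|
| 0.9 | 0.40 | 1.018 |
| 0.8 | 0.39 | 1.039 |
| 0.7 | 0.37 | 1.063 |
| 0.5 | 0.33 | 1.125 |

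If the ratio moves the other way, the limits are the reciprocals: 1/1.018 = 0.98 to 1/1.125 = 0.89. The direction is therefore unknown too.

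**Outside the band.** Early shares of 60% and 40% mean a 2.25-fold change in odds, and B = 1.02 (R = 0.9) to 1.14 (R = 0.5). Shares of 70% and 30% mean a 5.4-fold change, and B = 1.04 to 1.31.

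**Against the planned precision.** With 104.4 and 52.2 malignancies, the SE of the log rate ratio is √(1/104.4 + 1/52.2) = 0.170, so the 95% interval is the estimate multiplied or divided by exp(1.96 × 0.170) = 1.39. The 3000:2400 line gives the same SE. With that SE, the 3000:2400 example raises the two-sided false-positive rate from 5% to 5.1% (R = 0.9), 5.5% (0.8), 6.3% (0.7) or 10.3% (0.5). The documents give no serious-infection rate, so the same step cannot be done for that endpoint.

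**Does the remedy work?** Use the pooled incidence ratio of SAP 8.1.6 with period of start as the stratum. With no drug effect, a_i = λ_i PT1i and b_i = λ_i PT0i, so numerator and denominator both equal Σ λ_i PT1i PT0i/T_i. The ratio is 1.00 in every scenario above.

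**The case against.** The plan already has real protection. The common period is required more than once. The comparative set takes only patients with scheduled 3-year observation (SAP 5.1.2), so later Xeljanz patients followed for 6 months are out. The contract ratio favours roughly parallel enrolment. Section 6.3 contains prophylaxis against tuberculosis, pneumocystis pneumonia and hepatitis B for serious infection, and many patient characteristics, so drift acting through these is partly adjusted for. The tests are exploratory (SAP section 4), and section 6.3 allows covariates to be added by revision.

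Most of this stands, and it reduces the concern without closing it. The contract ratio governs contracted numbers in principle, not pace. DAS28 and the blood counts, which might have absorbed a change in patient selection, are scheduled only for the Xeljanz group (Protocol section 7). Drift in reporting or in unmeasured practice is not covered by any listed covariate.

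A reader might also infer more than the documents support:

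- That the plan expects unequal filling. It only provides for it, conditionally.
- That no between-group analysis uses calendar time. The SAP revision table places the between-group sensitivity analyses in section 8.2.3.1.4, and the text after 8.2.3.1.3 is blacked out. The statement can be made only for the visible text.
- That registration certainly ran for several years. Protocol section 5 gives no length.
- That the June 2014 revision of the use guideline shows practice drifted. The documents do not say what changed.

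**Conclusion.** The gap is real in the visible plan, and modest. The SAP accounts for calendar year against the general population but not in the between-group Cox, propensity-score (IPTW) or pooled estimates. Whether this biases the result depends on two things the documents do not show: different start-date distributions in the two groups, and drift that the listed covariates leave unadjusted.

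If the group ratio stays inside the contract band, the crude bias is at most about 1.02 to 1.12 for R from 0.9 to 0.5, or the reciprocal in the other direction. These are upper figures before covariate adjustment and lie well inside the malignancy interval factor of 1.39. Bias of 1.3 needs both strongly uneven accrual and a halving of the event rate, and nothing in the documents supports that combination. The case is stronger for serious infection than for malignancy, for which the documents suggest no mechanism of drift within the window.

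**What to change.** Add calendar year of start (or a coarser period if some years are sparse) to SAP section 6.3 for both endpoints. It then enters the propensity score, the Cox models, the strata of the pooled ratios and the standardized-difference table. Take the date from Day 1 as defined in SAP Appendix 11.1.1, the first recorded administration, because registration item [7] holds only the scheduled date for Xeljanz patients. Tabulate starts by year and group. If the two distributions agree, that table alone largely settles the matter.

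The cost is SAP wording, one more covariate and slightly wider intervals; no new data are needed. SAP version 10.0 already follows the database release, so the addition should be dated and its estimates shown beside those without the term.

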#### (2) Pre-treatment observation

##### [8] Contraindication (presence/absence of contraindication)

##### [9] Tuberculosis check (imaging diagnosis/tuberculin test/interferon $\gamma$ measurement (Quantiferon test, T-SPOT test, etc.)/antituberculosis drug administration)

The results of tests within 3 months prior to the start of treatment should be recorded before the treatment.

\*Patients with concurrent or suspected tuberculosis should be given appropriate antituberculosis drug.

